3.3 Selection of the comparison group and identification assumptions

An issue that arises is that while we can identify members of this group in the intervention arm of the study by asking for the details of those who receive additional support at six monthly intervals, we cannot identify members in the control arm because there are no set parameters regarding who would be eligible for additional support. As such, we do not have two randomised groups to compare. To address this, we propose to use a matching approach for the quasi-experimental design. Among different matching approaches, Propensity Score Matching (PSM) is the first choice to derive an appropriate group for comparison, although other approaches will be tested for robustness, as further elaborated in section 3.4.3 below.

As [Stuart \(2010\)](#) discussed, exact matching is the ideal scenario, but similar to Mahalanobis distance measures, its performance declines as the number of covariates increases. Requiring exact matches also often results in many unmatched observations, potentially introducing greater bias than allowing more inexact matches. The coarsened exact matching (CEM) approach can perform exact matching on a broader range of variables ([Black, Lalkiya, & Lerner, 2020](#)), although its precision decreases with non-informative covariates. Mahalanobis distance matching tends to be effective with a small number of covariates —less than 8, as noted by [Rubin \(1979\) and Zhao \(2004\)](#)— but its performance suffers when covariates deviate from normality or when dealing with numerous covariates ([Gu & Rosenbaum, 1993](#)). This decline likely stems from Mahalanobis matching and treating all interactions among pre-treatment variables with equal importance, which becomes increasingly complex as the number of covariates grows.

Since the literature is inconclusive on which algorithm is superior, given that each has relative strengths and weaknesses, a robust approach is implementing propensity score matching (PSM) along with other matching methods for comparison ([Morgan & Winship, 2015](#)). PSM is particularly effective in dealing with many covariates and large samples, increasing the likelihood of finding suitable matches.

The propensity score is the probability of receiving the intervention conditional on measured participant covariates. It is, in essence, a balancing score. If we have two populations, the intervention and control populations, both of which have a similar propensity score, the distribution of baseline covariates will be the same in the intervention and control groups. Hence, we can remove confounding effects by comparing participants who share a propensity score. This is analogous to that induced by randomisation in RCTs.

For the propensity score, the covariates for the matching will be socio-demographic variables such as sex, age, ethnicity, FSM, attendance, exclusions, suspensions and pre-test outcomes for the primary and secondary outcomes. As is often the case in PSM, the selection of the variables will depend on which model delivers the best balance in the matched sample.

A counterfactual control group will be derived using PSM to draw causal inferences of the relative effect of the intervention. A probit regression model will be employed. Callipers of width 0.2 of the standard deviation of the width of the logit propensity score will be employed to maximise matching. Once the propensity scores have been generated, they will be incorporated into the primary and secondary analysis using inverse propensity score weights (IPSW), because this will reduce the sample size required for the control group. One potential limitation of weighting approaches, akin to Horvitz-Thompson's estimation, is the potential for a substantial increase in variance when dealing with extreme weights (i.e. when estimated propensity scores approach 0 or 1). This increased variance is justified if the model is

appropriately specified and the weights are accurate. However, a concern arises when some extreme weights are more closely linked to the estimation process rather than the true underlying probabilities. To mitigate the impact of extreme weights, we would consider weight trimming as a solution, whereby weights exceeding a certain maximum value are capped at that maximum (Stuart, 2010). Robustness check through other matching techniques will allow us to test the sensitivity of this approach to increase in variance. Other matching approaches will include exact matching, Nearest-Neighbour matching, Mahalanobis distance, PSM with different calliper widths, and CEM, as discussed further in section 3.4.3 below.

The success of matching in reducing the imbalance of covariates will be reported by displaying the imbalance before and after matching, that is, between the unmatched and matched samples. The reduction of imbalance will be measured through the reduction in mean and median standardised bias and Rubin's B and Rubin's R. As discussed in Caliendo and Kopeinig (2008), a reduction to a standardised bias between below 2% to 5% is a good sign. Regarding Rubin's metrics, we will consider $B < 25$ and R between 0.5 and 2 enough balance (Rubin, 2001).

Finally, as acknowledged in the literature, the main limitation of all matching approaches is the inability to control for unobservable covariates (Abadie & Imbens, 2006; Morgan & Winship, 2015). While we have carefully controlled for observable factors through the matching process, there may be unobserved variables, such as student motivation or parental involvement, that could influence the outcome. However, by employing a rigorous matching strategy and drawing from a comprehensive set of observed covariates, we aim to mitigate the potential impact of unobservable confounders as much as possible.

3.4 Analysis

The primary **research question** is:

- What is the mean difference in externalising behaviour, measured by the Strengths and Difficulties Questionnaire (SDQ) subdomains of Conduct Problems and Hyperactivity, between CYP in intervention settings receiving TISUK training and CYP in control settings receiving business as usual at follow-up?

The secondary **research questions** are:

- What is the mean difference in internalising behaviour, measured by the Strengths and Difficulties Questionnaire (SDQ) subdomains of Emotional Problems and Peer Problems, between CYP in intervention settings receiving TISUK training and CYP in control settings receiving business at follow-up?

- What is the mean difference in prosocial behaviour, measured by the Strengths and Difficulties Questionnaire (SDQ) subdomain of Prosocial behaviour, between CYP in intervention settings receiving TISUK training and CYP in control settings receiving business-as-usual at follow-up?
- What is the mean difference in Total Difficulties, measured by the Strengths and Difficulties Questionnaire (SDQ) subdomain of Conduct Problems, Hyperactivity, Emotional Problems and Peer Problems, between CYP in intervention settings receiving TISUK training and CYP in control settings receiving business-as-usual at follow-up?
- What is the mean difference in non-psychotic psychological distress, measured by the General Health Questionnaire (GHQ), between CYP in intervention settings receiving TISUK training and CYP in control settings receiving business as usual at follow-up?
- What is the mean difference in well-being, measured by the Short Warwick Edinburgh Well-being Scale (SWEMWBS), between CYP in intervention settings receiving TISUK training and CYP in control settings receiving business as usual at follow-up?
- What is the mean difference in the sense of connectedness, measured by the School Connectedness Scale, between CYP in intervention settings receiving TISUK training and CYP in control settings receiving business as usual at follow-up?
- What is the mean difference in the percentage of exclusion between CYP in intervention settings receiving TISUK training and CYP in control settings receiving business as usual at follow-up?
- What is the mean difference in the percentage of suspensions between CYP in intervention settings receiving TISUK training and CYP in control settings receiving business as usual at follow-up?
- What is the mean difference in the percentage of attendance between CYP in intervention settings receiving TISUK training and CYP in control settings receiving business as usual at follow-up?
- What is the mean difference in all primary and secondary CYP outcomes between CYP in intervention settings who received TISUK training and CYP in control settings who received business as usual, considering sub-group analysis by sex, ethnicity, and free school meal (FSM) eligibility?

The analysis will be conducted using an intention to treat (ITT) and include all available data, maintaining participants as members of their allocated group.

3.4.1 Primary analysis

The primary analysis will likely be a linear regression model adjusted for baseline stratification covariates (proportion FSM), and the baseline value of the outcome. As there is variation in

business as usual (BAU) across sites, a multilevel model will be estimated to account for pupils being nested within schools. Individual outcomes will be incorporated into the model with an inverse propensity weight for each participant.

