3.1 Design overview

A QED study, using a propensity score matching design, will be embedded within this trial to examine the targeted element of the intervention. In the intervention arm, some staff are given advanced training (Diploma level) to identify a more vulnerable CYP subgroup and provide extra targeted support. This individual intervention is estimated to be provided to about 75 CYP per school, 15 CYP per year group. In the main trial analysis, this group of CYP in Year 8 would become subsumed into the overall intervention group, with all baseline and follow-up data collected on outcomes included in the main trial. Staff who participate in the diploma training will already have identified most young people who would potentially benefit from more intensive support and, in the early stages of training, will be provided with tools to identify any additional young people. By the time of follow-up, at 15 months, this cohort of young people would have been identified and received at least nine months of intervention.

Assuming this group of vulnerable young people is about 15 per school, with a consent rate of 80%, the effective sample size will be 12 per school. Assuming our original aim of 100 schools in the trial, this gives 1,200 CYP across all schools, 600 in the treatment arm matched to 600 in the control arm.

The outcomes for this study will be the same individual pupil-level primary and secondary outcomes as for the main trial, for those that are provided with this individual or small group support in Year 8: the primary outcome is externalising behaviour at pupil level measured by the Strengths and Difficulties Questionnaires (SDQ) – Combined Conduct and Hyperactivity Scale. The secondary outcomes at pupil levels consist of internalising behaviour, prosocial behaviours, total difficulties, non-psychotic psychological distress, well-being, sense of connectedness, exclusions and suspensions, and school attendance.

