3.2 Sample size calculations

Sample size estimation and assumptions

The sample size calculation is designed to detect a difference of 0.2, YEF's expected maximum MDES value for efficacy evaluations. To detect this difference with 80% power, an alpha of 0.05 and a two-sided test, at least 527 CYP in each group are required, totalling 1,054 CYP.

For the PSM, the sample size estimations starts from the assumption of 15 CYP on average per school at baseline, assuming a follow-up rate of 80% to account for attrition and consent. The harmonic mean of CYP per year group receiving more intensive support is estimated to be 15. Using this and an ICC of 0.03, the estimated clustered design effect is 1.45. This inflates our required sample to 1,528. With 100 schools, 15 participants per class provide a sample of 1500. Incorporating the inverse propensity score weights will reduce the size of the overall sample by a conservative estimate of 30%, resulting in a required sample of 1,070.

Table 7 indicates the impact of different group sizes (pupils per cluster) on the number of schools needed in the intervention arm of the PSM analysis. The table shows that with 15 pupils per cluster, data from at least 36 intervention schools are required. At the lower end, with 10 pupils per cluster, data from 48 schools would be required. If the follow-up rate is 80% as anticipated, 12 pupils per school will be available, requiring circa 42 schools in each arm of the study. While the target is to maintain 50 schools in each arm, these conservative estimates should be considered.

At the point where the PSM is conducted, the pre- and post-test correlation for the primary outcome can be estimated and incorporated into the sample size calculation, potentially adjusting the required sample size.

Table 7 Impact of differential cluster size on the proportion of schools retained for the intervention group

Pupils	15	14	13	12	11	10
Base sample	527	527	527	527	527	527
Design effect (DE)	1.45	1.42	1.39	1.36	1.33	1.30
Adjusted sample	764	748	733	717	701	685
Sample adjusted for IPW	535	524	513	502	491	480
Number of intervention schools	36	37	39	42	45	48

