3.4.3 Robustness Checks

Several robustness checks will be implemented, including the following:

- We will test the common support in the matched sample and the t-test after matching to analyse if the matching is satisfactory, including reviewing the B and R – Rubin to ensure that the matching matches at least well.
- Use Rosenbaum (2002) to evaluate to what extent the ATE estimate is robust to non-compliance with the assumption of selection in observables.
- Measure the sensitivity to the matching method to test the robustness of the main matching technique one-to-one. Different forms of matching will be estimated: (a) calliper (with different widths), (b) nearest neighbour (NN) (tested with five neighbours), and finally, (iii) kernel. The choice of the matching method will be transparently discussed and linked to the present evaluation.
- Estimate the results using the Inverse Probability Weighting (IPW) methodology and Entropy Balancing.
- We will first apply the balance test proposed by Smith and Todd (2005) based on the regression of the covariates against the treatment variable (T) and its polynomial forms, where $p(X)$ rejecting the null hypothesis would imply that the variables X_j are unbalanced between the groups. Second, we will implement a Kolmogorov-Smirnov test to ensure a balance between both groups.
- We will consider, if applicable, the falsification test proposed by Lee and Lemieux (2010)). This test seeks to test the hypothesis that the average effect is zero in covariates or in pseudo-outcomes on which - by definition - no effect of the treatment.

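### On its natural reading, the QED matches pupils one-to-one and then weights them by the inverse of the same propensity score, which re-creates the imbalance that matching removed

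*SAP*

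**What the plan says.** SAP 3.3 derives a counterfactual control group by propensity score matching, using a probit model and a calliper of 0.2 SD of the logit score. It then says of the scores that "they will be incorporated into the primary and secondary analysis using inverse propensity score weights (IPSW". SAP 3.4.1 repeats this for the primary model: "Individual outcomes will be incorporated into the model with an inverse propensity weight for each participant". SAP 3.4.4 handles the secondary outcomes in a similar way, and Protocol Appendix 2 has the same sequence.

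Three places point to a one-to-one matched analysis set:

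- SAP 3.1 describes "600 in the treatment arm matched to 600 in the control arm".
- SAP 3.4.3 sets out to "test the robustness of the main matching technique one-to-one".
- SAP 3.4.5 says that the matched sample yields the average treatment effect on the treated (ATET).

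Weighting on its own is listed separately, as a robustness check: "Estimate the results using the Inverse Probability Weighting (IPW) methodology and Entropy Balancing".

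Balance is to be shown before and after matching, "that is, between the unmatched and matched samples". The outcome model in 3.4.1 adjusts for FSM and the baseline value of the outcome. The matching covariates in 3.3 go further: demographics, attendance, exclusions, suspensions and all the pre-tests. No weight formula is given, and no section says outright which pupils enter the weighted model.

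**The concern.** Matching and inverse weighting are alternative ways to remove the same confounding. Once supported and control pupils are paired on the score, the two groups share one score distribution and nothing is left for the weights to correct. Applying them anyway pulls the groups apart again. The supported pupils least likely to have been selected receive the largest weights, while control weights barely vary or rise with risk.

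The SAP describes the supported group as more vulnerable, so the distortion makes that group look better than its controls. Adjustment for the baseline SDQ score deals with that one covariate. Imbalance in attendance, exclusions, suspensions and the other pre-tests passes into the estimate. At stake is the only planned estimate of the effect of targeted support, which could show a false benefit beside a clean balance table.

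**Working it through.** **1. The plan's own figure.** SAP 3.2 states: "The sample size calculation is designed to detect a difference of 0.2", with "80% power, an alpha of 0.05 and a two-sided test". SAP Table 8 (Randomisation column) gives 40 + 38 = 78 schools, 12 pupils per school, ICC 0.015 and MDES 0.20. The formula in SAP 2.2, without covariates, is

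MDES = M × √[ρ/(P(1−P)J) + (1−ρ)/(P(1−P)Jm)]

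- P = 40/78 = 0.5128, so P(1−P)J = 19.49.
- M on 76 df = 1.992 + 0.846 = 2.838.
- MDES = 2.838 × √(0.000770 + 0.004212) = 2.838 × 0.0706 = 0.200.

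The figure reproduces, with no gain from weighting in it.

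**2. Why stacking fails.** Let e be the propensity score and f(e) its density in the matched sample, the same in both arms.

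| Weights on the matched set | Supported | Control |
|---|---|---|
| None | f(e) | f(e) |
| 1/e and 1/(1−e) | f(e)/e | f(e)/(1−e) |
| ATT: 1 and e/(1−e) | f(e) | f(e)·e/(1−e) |

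In rows 2 and 3 the ratio of supported to control density is (1−e)/e, up to a constant. It falls as e rises, so whenever e varies the supported group is tilted towards lower risk than the controls. This needs no assumption about the outcome.

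**3. Size, by simulation under a true null (1,000 replicates per scenario).** From the documents: 40 v 38 schools, 166 pupils per school (SAP Table 4), ICC 0.015, 12 supported pupils per intervention school, probit score, 1:1 matching with a 0.2 SD logit calliper, and adjustment for school FSM and baseline outcome. Weighted regression with school-clustered standard errors stands in for the weighted multilevel model.

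Assumed, because the documents do not give them: log-odds of selection per SD of 0.5 to 1 on baseline score and 0 to 1 on the other covariates, and an outcome coefficient of 0 to 0.3 for the other covariates.

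Standardised differences are 0.00 after matching. After adding 1/e and 1/(1−e) they are −0.7 to −1.3 on baseline score and −0.4 to −1.3 on the other covariates. Two-sided rejection, with log-odds 1 on baseline score:

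| Log-odds, other covariates | Outcome coefficient | Matched, unweighted | Matched + 1/e, 1/(1−e) | Mean estimate (true value 0) | Matched + ATT weights |
|---|---|---|---|---|---|
| 0.5 | 0.1 | 5.3% | 8.8% | −0.032 | 8.4% |
| 0.5 | 0.2 | 4.7% | 20.0% | −0.069 | 15.5% |
| 0.5 | 0.3 | 4.5% | 33.5% | −0.104 | 27.2% |
| 1 | 0 | 5.8% | 7.6% | +0.003 | 5.8% |
| 1 | 0.1 | 5.5% | 15.9% | −0.065 | 13.4% |
| 1 | 0.2 | 5.1% | 43.9% | −0.133 | 35.6% |
| 1 | 0.3 | 5.1% | 66.7% | −0.201 | 59.8% |

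The excess rejections nearly all favour TISUK (43.6 of the 43.9 points in the sixth row). The Monte Carlo standard error is √(0.05 × 0.95/1,000) = 0.7 points at 5% and √(0.44 × 0.56/1,000) = 1.6 points at 44%.

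Over all scenarios run:

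- Selection on baseline score alone: 4.6–5.3%.
- Other covariates drive selection but have coefficient 0: 5.3–7.6%.
- Treated weights capped at the 90th percentile: 9–16% at coefficient 0.1 and 20–46% at 0.2, so capping is no cure.
- Matched, unweighted: 3.5–5.9%.
- ATT weights on all control-arm pupils, no matching: 4.6–5.8%.
- Score re-estimated inside the matched set before weighting: 3.0–6.0%.
- 1/e and 1/(1−e) on all control-arm pupils, no matching: 6–14%, with imbalance of at most about 0.11 SD. This comes mainly from extreme weights; in the two selection settings tabulated, the effective number of supported pupils falls from 480 to 102 and 54.

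**The case against.** The strongest reply is that the SAP never confines the weighted model to the matched pairs. SAP 3.4 says that all available data will be used, and 3.3 discusses Horvitz-Thompson estimation, extreme weights and trimming, which is full-sample language. The unequal arm counts in Table 8 (456 and 480) cannot be one-to-one pairs, and 600 to 600 is planning arithmetic (12 × 50). Re-estimating the score after matching would also remove the fault. All of this stands as ambiguity, and the finding is therefore tied to a reading.

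It does not rescue the text. On the full-sample reading, weights of 1/e and 1/(1−e) do not target the ATET named in 3.4.5, and the matched-sample balance checks describe a sample other than the one analysed. The estimand label is itself uneven: Protocol Appendix 2 and the Rosenbaum item in SAP 3.4.3 speak of the ATE. Neither document mentions re-estimating the score.

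A reader might infer that the imbalance could not be detected. That goes too far. SAP 3.4.3 plans Smith-Todd and Kolmogorov-Smirnov balance tests, other matching methods, IPW and entropy balancing and, if applicable, a falsification test on covariates. Any of these might expose a divergent result. None is specified for the matched-and-weighted sample, so the reporting gap remains.

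**Conclusion.** Wrong as written on the natural reading, and under-specified on the other. That stacking re-creates imbalance is algebra. That it favours TISUK and inflates false positives holds if the non-baseline matching covariates both drive selection and predict follow-up beyond the baseline score. Under assumed coefficients of 0.1 to 0.2, rejection of a true null is about 9–44% against 5%.

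A reader might want a single inflation factor. The documents do not support one: they give neither selection strength nor prognostic strength, and the range explored runs from about 1 to 13 times nominal (66.7/5 = 13.3 at the top). There is little or no inflation if those covariates are not prognostic or selection depends on baseline score alone. Nor does the finding say that weighting is unsound in itself, since ATT weighting without matching holds its level. The randomised comparison is unaffected. The simulation uses 40 intervention schools; SAP 2.2 reports four intervention dropouts, so the supported group may be smaller.

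**What to change.** In SAP 3.3, 3.4.1 and 3.4.4 and Protocol Appendix 2, use one adjustment for the primary and secondary QED models:

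- **Either** fit them unweighted in the one-to-one matched sample, which agrees with 3.4.3, 3.4.5 and the Rosenbaum bounds, and keep IPW on the full unmatched sample as the robustness check already listed.
- **Or** use ATT weights on all eligible pupils, without matching.

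With either, state the analysis set, the weight formula and the estimand. For every estimate, report standardised differences in the exact sample and with the exact weights used.

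The cost is wording; no new data are needed. If matching without weights is chosen, the claimed 30% saving in SAP 3.2 must go. The requirement then returns from 1,070 to 1,528 (1,054 × 1.45), against 936 expected in Table 8. The 12-pupil column of Table 7 becomes 717/12 = 59.75, or 60 intervention schools instead of 42. Those figures need revisiting anyway. At 0.2 SD and 80% power, 2 × (1.960 + 0.842)²/0.04 gives 393 per group; the stated 527 corresponds to about 90% power. The Table 8 MDES of 0.20 contains no weighting gain and does not change.
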